In order to define the sample size, we carried out an exploratory study enrolling 20 patients in each group. Mean gastric cleanliness score in the position change and conventional groups were 20.1 and 19.4, respectively. This study was a superiority study based on two-sided alpha as 0.05 and the power as 80%, thus 64 patients (32 patients in each group) were required by using NCSS-PASS 11 program (version 11.0.7, NCSS, Kaysville, Utah, USA). Considering a withdrawal rate of 20%, we enrolled 80 patients at least. Statistical analysis was performed using SPSS Statistics software version 18.0. Descriptive statistics were given as means ± standard deviation (SD). Differences in categorical variables between patient groups were compared by using the Chi-square test; differences in means were compared with the independent *t*-test. In GCS comparison and subgroup analysis which lack of normal distribution for quantitative data, we used Mann-Whitney test for comparison of the two groups. A *P*-value of < 0.05 was considered to be statistically significant.

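### Does testing GCS with Mann-Whitney, after sizing the trial on mean GCS, require a different primary analysis?

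*SAP*

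**What the plan says.** The whole statistical plan is one paragraph in the SAP. Its sample-size inputs are pilot means: "Mean gastric cleanliness score in the position change and conventional groups were 20.1 and 19.4, respectively". From these, with a two-sided 5% level and 80% power, "thus 64 patients (32 patients in each group) were required by using NCSS-PASS 11 program". Results are to be described by mean and SD. The general rule for quantitative data is that "differences in means were compared with the independent" t-test. GCS is treated separately: "In GCS comparison and subgroup analysis which lack of normal distribution for quantitative data, we used Mann-Whitney test". Significance is P below 0.05. No between-group effect measure or interval is named, and no SD is given.

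The Protocol (Outcome parameters, Primary Outcome Measure) defines GCS as the sum of six landmark grades, each scored 1 to 4. The total runs from 6 to 24, and 18 or more counts as acceptable. The Protocol gives no summary measure for comparing the arms.

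**The concern.** The primary outcome appears in two currencies. It is sized and described in points on a mean scale, where the implied difference is 20.1 − 19.4 = 0.7, but it is tested on ranks. Mann-Whitney asks whether a patient in one arm tends to score higher than a patient in the other. That matches a comparison of means when one distribution is a shifted copy of the other, and need not do so otherwise. If position change helped most patients a little but left a few badly prepared, the rank test could declare superiority with no gain in mean score.

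Two further features add to the unease. The reason given for the rank test is the distribution of the data, which suggests a choice made after looking. And a rank P-value does not say how many points are gained on a scale spanning 24 − 6 = 18.

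**Working it through.** **1. The plan's own figure.** Inputs: difference 0.7, two-sided alpha 0.05, power 80%, 32 per arm. The SD is not given, so 64 cannot be reproduced and the SD has to be back-solved:

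- Normal approximation: SD = 0.7 × √(32/2) / (1.96 + 0.84) = 2.8 / 2.80 = 1.00.
- t-test: the standardised difference is 0.711, so SD = 0.7 / 0.711 = 0.98.

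The withdrawal step reproduces: 64 / (1 − 0.20) = 80. The SAP does not name the PASS procedure, so t-test sizing is an inference.

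**2. Cost of the rank test against that sizing.** The asymptotic efficiency of Mann-Whitney relative to the t-test is 3/π = 0.955 for normal data and 0.864 in the worst pure-shift case.

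- Normal data: 32 / 0.955 = 33.5, so 34 per arm.
- Worst case: 32 / 0.864 = 37.04, so 38 per arm.

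Enrolment is 40 per arm before withdrawals.

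**3. Behaviour of the two tests.** All shapes below are assumed, because the documents give no distribution. Entries are the percentage of simulated trials with P < 0.05. Simulation error and details of rounding move them by a point or two.

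| Assumed truth | Per arm | Test of means | Mann-Whitney |
|---|---|---|---|
| Normal, SD 0.98, means 20.1 and 19.4 | 32 | 79.8 (t) | 78.4 |
| The same, rounded to whole scores | 32 | 77.2 (t) | 75.5 |
| Equal means, tail in position-change arm only | 40 | 5.5 (Welch) | 27.4 |
| Equal means of 20.0, SD 3.2 skewed against SD 1.0 | 40 | 5.7 (t) | 29.3 |
| Equal means, SDs 1.8 and 3.4 | 40 | 5 (Welch) | 12 |
| Equal means, SDs 0.8 and 1.2 | 40 | about 5 (Welch) | 5.0 |
| 10% tail in both arms, SD 1.2, shift 0.7 | 40 | 25 (Welch) | 50 |
| 5% tail in both arms, SD 1.0, shift 0.7 | 40 | 42 (Welch) | 73 |
| 10% tail in both arms, no shift | 40 | about 5 (Welch) | about 5 |

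In the one-arm tail case, 90% of position-change patients have mean 20.1 and 10% have mean 13.1. The arm mean is 0.9 × 20.1 + 0.1 × 13.1 = 18.09 + 1.31 = 19.40, equal to the control mean. The probability that a position-change patient scores higher is 0.59, not 0.50. Mann-Whitney is therefore rejecting its own null correctly. It disagrees with the comparison of means because it answers a different question.

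**4. Whether a difference in points can be recovered.** With arm means, SDs and numbers, an approximate 95% interval is the difference ± 1.96 × √(SD₁²/n₁ + SD₂²/n₂). At SD 0.98 and 32 per arm the standard error is 0.98 × √(2/32) = 0.245 and the half-width is 1.96 × 0.245 = 0.48. A 0.7-point difference would then carry an interval of about 0.22 to 1.18.

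**The case for a change.** The strongest case for a change is that size and precision of benefit are what a reader needs from this trial. Both pilot means already exceed the acceptable cut-off of 18, so a bare P-value says little about usefulness. A bounded score with means in its upper part can plausibly differ in spread between arms, and then the planned test and the planned summaries may point in different directions. A prespecified mean difference with an interval would cost one line of text.

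Part of this stands. The SAP does not align its mean-based sizing with its rank-based test, and naming an effect measure with a 95% interval (mean difference, Hodges-Lehmann shift or probability of superiority) would be good practice.

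The rest is weaker.

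- The SAP assigns one test to the GCS comparison. It gives a distributional reason but no rule for switching between tests. Its past tense leaves the timing of the choice open, which is not evidence of a data-driven choice.
- The 0.7-point target is derived from the pilot means and is not written as a hypothesis.
- The large disagreements need strongly unequal shapes, which nothing in the documents suggests. With SDs near the back-solved value of 1, such as 0.8 and 1.2, Mann-Whitney stays at 5.0%.
- Where GCS is non-normal in the same way in both arms, Welch can have about half the power of the rank test.

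**Conclusion.** No change to the plan is called for. Mann-Whitney is a valid superiority test for a sum of six ordinal grades, and under a common shape it addresses the same shift as the t-test. Its cost against mean-based sizing is 34 rather than 32 per arm on normal data, or 79.8 − 78.4 = 1.4 percentage points of power at 32 per arm. Replacing it with Welch would be a judgement call. It protects against unequal shapes (5.5% against 27.4% rejection at equal means) and can lose substantial power under a shared tail (25% against 50%). The documents do not show which situation applies.

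The absent effect measure is a gap that analysts fill sensibly, since the planned means and SDs yield a difference and an approximate interval. These conclusions rest on assumed score distributions and on an SD near 1 back-solved from 32 per arm. The missing SD is a separate matter for the sample-size justification.

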Secondary outcomes included detection rate of positive findings, number of lesions per patient (NLPP), gastric examination time, and safety of MCCG. Positive findings defined as any pathology detected by MCCG, including polyp, ulcer, gastric fundus varices, submucosal tumor, and carditis. The diffuse lesions such as superficial, atrophic, and erosive gastritis were defined as negative findings [6]. NLPP was defined as the number of positive findings divided by the total number of patients, the location of NLPP were also recorded. Gastric examination time was determined using digital stopwatch in the ESNavi software. Safety of MCCG, or adverse events, defined as symptoms or signs such as abdominal distention, nausea, or vomiting, were monitored closely during the MCCG procedure. Capsule retention (i.e., a capsule endoscope remaining in the gastrointestinal tract for more than two weeks or a capsule endoscope that requires directed intervention or therapy to aid its expulsion) was monitored and followed up for up to two weeks.

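### Subgroups are analysed by Mann-Whitney comparison of the arms at P<0.05 with no treatment-by-subgroup interaction test, so the plan cannot show whether the effect differs between subgroups

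*SAP*

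**What the plan says.** The SAP is one unnumbered paragraph on sample size and analysis. Its only statement about subgroups is "In GCS comparison and subgroup analysis which lack of normal distribution for quantitative data, we used Mann-Whitney test for comparison of the two groups". The decision threshold, given once for all tests, is a P-value below "0.05 was considered to be statistically significant".

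Neither document names the subgroups, says how many there are, labels them exploratory, provides an interaction test, or says how subgroup results will be interpreted.

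The trial was sized on total GCS alone: "Mean gastric cleanliness score in the position change and conventional groups were 20.1 and 19.4, respectively", with "two-sided alpha as 0.05 and the power as 80" per cent, and "thus 64 patients (32 patients in each group) were required by using NCSS-PASS 11 program". Allowing for 20% withdrawal, the enrolment target is at least 80. The SD behind the calculation is not given.

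**The concern.** The usual reason for a subgroup analysis is to ask whether treatment works better in some patients than in others. That is a question about the difference between two treatment effects. The planned test compares the arms, so within a subgroup it addresses one effect at a time. A P-value below 0.05 in one subgroup and above it in another is not evidence that the effects differ, because the smaller samples alone make such splits common. Naming the subgroups would not cure this, since the test answers a different question.

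What is at stake is a reader concluding that position change helps only some patients when the benefit is the same in all. The primary comparison of total GCS is not affected.

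**Working it through.** **Inputs from the SAP and Protocol.** Means 20.1 and 19.4, difference 0.7; two-sided alpha 0.05; power 80%; 32 per group; 20% withdrawal; 1:1 allocation.

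**Assumptions, because the documents are silent.** The SD; two subgroups that do not overlap; their relative size; the same true effect in both.

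**1. The plan's own figures.** 64/(1 − 0.20) = 80, which matches. The 64 cannot be reproduced without an SD. Solving the noncentral-t power equation for 32 per group at 80% gives a standardized effect of 0.7115, so SD = 0.7/0.7115 = 0.984. The normal approximation gives 0.999.

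**2. Power inside one of two equal subgroups.** The noncentrality is 0.7115 × √(n/2), with n patients per arm in the subgroup.
- 32 per arm overall, n = 16: 0.7115 × √8 = 2.012; critical t (30 df) 2.042; power 0.495.
- 40 per arm overall (no withdrawals), n = 20: 0.7115 × √10 = 2.250; critical t (38 df) 2.024; power 0.592.

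**3. Chance that exactly one subgroup reaches P<0.05.** With powers p₁ and p₂ in independent subgroups, this is p₁(1 − p₂) + p₂(1 − p₁).
- n = 16: 2 × 0.495 × 0.505 = 0.50.
- n = 20: 2 × 0.592 × 0.408 = 0.48.

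**4. Check with the planned test.** Mann-Whitney tests on simulated integer-rounded scores (5,000 trials per setting) gave 0.50 at 32 per arm and 0.49 at 40 per arm. Among trials whose overall comparison was significant, the figures were 0.59 and 0.55. A treatment-by-subgroup interaction test on the same data rejected in 5.0% of trials in both settings.

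**5. Unequal subgroups, same effect (t-based).**

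| Split | Overall n per arm | p₁ | p₂ | Exactly one |
|---|---|---|---|---|
| 75/25 | 32 | 0.675 | 0.264 | 0.58 |
| 75/25 | 40 | 0.773 | 0.325 | 0.60 |
| 90/10 | 32 | 0.756 | 0.111 | 0.70 |
| 90/10 | 40 | 0.845 | 0.137 | 0.75 |

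**6. Other true effect sizes, equal split (normal approximation).** If true overall power is P, the overall noncentrality is 1.96 + z(P), and each half has that value divided by √2. At P = 0.99: (1.96 + 2.326)/√2 = 3.031; power per half Φ(3.031 − 1.96) = 0.858; exactly one = 2 × 0.858 × 0.142 = 0.24. The same steps give 0.41 at P = 0.50, 0.50 at 0.80, 0.47 at 0.90 and 0.40 at 0.95. For a much weaker effect (P = 0.20) the figure is 0.22.

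**7. What an interaction test could detect.** With equal subgroups, the standard error of the difference between the two effects is twice that of the overall effect. At 32 per arm: 2 × 0.984 × √(2/32) = 0.492. If the effects truly differed by 0.7 points, z = 0.7/0.492 = 1.42 and power is about Φ(1.42 − 1.96) = 0.30. At 40 per arm: standard error 0.440, z = 1.59, power about 0.36.

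**The case against.** The strongest reply is that the SAP never says subgroup results will be contrasted. A reader might infer a rule that an effect significant in one subgroup only will be reported as confined to it. No such rule is written. So the 48-50% is the chance of split P-values. It becomes a false-claim rate, comparable with the interaction test's 5%, only if someone reads the split as a difference. This stands, and the point is limited accordingly: the plan leaves that misreading open and offers no test that would settle the question.

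The figure also depends on inputs the documents do not give: the SD and the number and size of the subgroups. That stands too, which is why it is stated with its assumptions and a range.

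Two further readings are tempting and should not be adopted.
- A reader might take subgroup to mean the six gastric landmarks and infer six separate tests. The Protocol's primary outcome section sums the landmarks into one score, and neither document plans a landmark-level test. Landmarks are also correlated measurements on the same patients, so the calculation above would not apply to them.
- A reader might infer that the single 0.05 threshold is a multiplicity error across secondary outcomes. The Protocol names one primary outcome, lists the secondary outcomes separately ("Secondary outcomes included detection rate of positive findings, number of lesions per patient (NLPP), gastric examination time, and safety of MCCG"), and the SAP sizes the trial on GCS alone. Leaving secondary P-values unadjusted beside one named primary is a common trade-off.

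Finally, an ordinary linear model fits poorly with the SAP's own statement that these data are not normally distributed. That is fair, and it affects the choice of interaction model. The low power of an interaction test is a real limit, but within-subgroup tests do not overcome it; they answer a different question.

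**Conclusion.** The concern holds in this limited form. The SAP commits to a subgroup analysis whose stated method cannot show whether the effect of position change differs between subgroups, and nothing else in the documents fills that gap.

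With two equal subgroups, a uniform 0.7-point effect and the back-solved SD of about 0.98, exactly one subgroup would reach P<0.05 in about 48-50% of trials. At the design effect this rises to 58-60% for a 75/25 split and 70-75% for 90/10. With equal subgroups it falls to about 24% if true overall power is 99%. An interaction test would wrongly signal a difference in about 5%. The result for total GCS is unaffected; only conclusions about who benefits would be unreliable.

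**What to change.** Replace the subgroup clause of the SAP with text to this effect: *The patient subgroups are [list], fixed before unblinding. A difference in treatment effect between subgroups will be judged only by the treatment-by-subgroup interaction term in a model of total GCS (an ordinal or rank-based model, or a linear model with robust standard errors). Within-subgroup differences will be shown with 95% confidence intervals and labelled exploratory; no claim of a differing effect will rest on comparing P-values between subgroups.* The Mann-Whitney test of total GCS can stay as it is.

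The cost is a change of wording and one model term, with no new data or patients. The downside is low power: about 30-36% even for a 0.7-point difference between the two subgroup effects (step 7). Subgroup claims will therefore become rarer, and the report should say that a non-significant interaction does not establish a uniform effect.
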